6.5. Missing Data

6.5.1. General Guidelines Regarding Handling of Missing Data

All attempts will be made to collect all data per the protocol. Efforts to minimize loss-to-follow-up will be considerable. Chart review will be performed for lost-to-follow-up subjects to obtain data related to the subjects' clinical status, oxygen use, or death status after discharge. However, small amounts of missing data may occur. In order to conduct mITT and ITT analyses for primary and secondary outcomes, missing data will be imputed in the manners described below in [Table 7](#). Prior to applying the imputation rules described in [Table 7](#), an endpoint review committee (ERC) may meet to adjudicate the primary endpoint and the key secondary endpoints for each study stage, such as Day 8 ordinal scores for subjects discharged to hospice, another hospital, or long-term care facilities. Any ERC reviews will be performed prior to database lock and all committee members will be blinded to treatment assignments. If an ERC is used, an ERC charter will be prepared prior to any reviews.

For the primary analysis of ordinal score at Day 8, the following imputations will be performed prior to multiple imputation:

- If a subject is discharged from the hospital to another location other than LTAC, hospice care or other hospital, has intermittent missing ordinal score and reported an ordinal score of 1 or 2 after the missing score then:
 - The intermittent missing ordinal score is imputed as 1 if the scores reported before and after the missing value are both 1 and no change in oxygen use or hospitalization status after discharge to a location other than hospice, long term acute care or other hospital.
 - The intermittent missing ordinal score is imputed as 2 after discharge to a location other than hospice, long term acute care or other hospital if the subject doesn't fall into the category above and subject is not hospitalized at the time point.
- LOCF will be used for remaining intermittent missingness of ordinal scores for the next planned assessment.
- All missing scores after death will be assigned an ordinal score of 8.
- Subjects that terminated from the study with known discharge to a location other than hospice, LTAC or other hospital at their last assessment will be assigned a score of 2 for all timepoints after last assessment.

Remaining missing ordinal scores for subjects that terminated early from the study and were still hospitalized at the time of their last assessment or with discharge to a location of hospice, LTAC or other hospital at the time of last contact will be imputed using multiple imputation. A sensitivity analysis of this analysis will be

performed using multiple imputation for all subjects missing ordinal after their last assessment regardless of their discharge status at the last assessment. Details of multiple Imputation are provided in Section 6.5.2.

Some analyses of ordinal score such as those reported in Table 17, Table 18, Table 20, Table 21, Table 24, Table 25, Table 26, Table 27, Table 34, Table 35, Figure 4, Figure 5, Figure 6, Figure 7, and Figure 18 will be based on complete ordinal score data created using the following steps:

- If a subject is discharged from the hospital to a location other than LTAC, Hospice care or other hospital, has intermittent missing ordinal score and reported an ordinal score of 1 or 2 after the missing score then:
 - Impute the intermittent missing ordinal score as 1 if the scores reported before and after the missing value are both 1 and no change in oxygen use or hospitalization status after discharge to a location other than hospice, long term acute care or other hospital.
 - Impute the intermittent missing ordinal score as 2 after discharge to a location other than hospice, long term acute care or other hospital if the subject doesn't fall into the category above and subject is not hospitalized at the time point.
- LOCF will be used for remaining intermittent missingness of ordinal scores for the next planned assessment.
- All missing scores after death will be assigned an ordinal score of 8.
- Subjects discharged from the hospital to a location other than LTAC, hospice care or other hospital at their last assessment will be assigned a score of 2 for all timepoints after last assessment.
- Impute all remaining missing data after last assessment using last observation carried forward.

Analysis of time to event endpoints (i.e., sustained recovery, time to improvement, time to mechanical ventilation or death) will be based on observed ordinal score without imputation along with discharge and death information. Refer to Table 7 for additional details regarding censoring and handling of missing data for all endpoints. As handling of missing data might differ for different stages of this study, stage-specific SAPs will provide additional details if handling of missing data for an endpoint for that stage differ from what is in the master SAP.

Table 7: Imputation Method for Each Endpoint and Analysis Type

Endpoint	Analysis	Imputation Method
Primary Endpoint		
1. Ordinal Score at Day 8	Primary	
 • If a subject is discharged from the hospital to another location other than LTAC, hospice care or other hospital, has intermittent missing ordinal score and reported an ordinal score of 1 or 2 after the missing score then: 
 ○ Impute the intermittent missing ordinal score as 1 if the scores reported before and after the missing value are both 1 and no change in oxygen use or hospitalization status after discharge to a location other than hospice, long term acute care or other hospital. ○ Impute the intermittent missing ordinal score as 2 after discharge to a location other than hospice, long term acute care or other hospital if the subject doesn't fall into the category above and subject is not hospitalized at the time point. • LOCF will be used for remaining intermittent missingness of ordinal scores for the next planned assessment. • All missing scores after death will be assigned an ordinal score of 8.

Endpoint	Analysis	Imputation Method
		
 Subjects discharged from the hospital to a location other than LTAC, hospice care or other hospital at their last assessment will be assigned a score of 2 for all timepoints after last assessment. Multiple imputation will be used to impute missing ordinal scores after last assessment for subjects still hospitalized or discharged to hospice, other hospital, or long-term care facility at their last assessment. See Section 6.5.2 for more details.
	Primary with Sensitivity Imputation 1	
 Use similar imputation methods for intermittent missingness and missing data after death. Multiple Imputation will be used for all subjects missing data after last assessment regardless of their discharge status at the last assessment.
	Primary with Sensitivity Imputation 2	
Use complete data defined as follow:
 
 If a subject is discharged from the hospital to another location other than LTAC, hospice care or other hospital, has intermittent missing ordinal score and reported an ordinal score of 1 or 2 after the missing score then: 
 Impute the intermittent missing ordinal score as 1 if the scores reported before and after the missing value are both 1 and no change in oxygen use or hospitalization status after discharge to a location other than hospice, long term acute care or other hospital. Impute the intermittent missing ordinal score as 2 after discharge to a location other than hospice, long term acute care or other hospital if the subject doesn't fall into the category above and subject is not hospitalized at the time point. LOCF will be used for remaining intermittent missingness of ordinal scores for the next planned assessment. All missing scores after death will be assigned an ordinal score of 8 Subjects discharged from the hospital to a location other than LTAC, hospice care or other hospital at their last assessment will be assigned a score of 2 for all timepoints after last assessment. Impute all remaining missing data after last assessment using last observation carried forward.
	Sensitivity	
 Same imputation as the primary analysis
	Supplemental	
 Same imputation as the primary analysis
	Subgroup	
 Repeat analysis for each subgroup using same imputation as primary analysis for this endpoint.
Key Secondary Endpoints		
1. Time to Sustained Recovery	Primary	
 Use the complete data for ordinal score to derive sustained recovery. Subjects whose last assessment in the study is prior to Day 57 (beginning of Day 60 window) will be considered not recovered and censored at the date of their last assessment. Death prior to recovery will be considered not recovered and censored at expected study Day 60.
	Primary with Sensitivity Imputation 1	
 Use the complete data for ordinal score to derive sustained recovery. Subjects whose last assessment in the study is prior to Day 57 (beginning of Day 60 window) after discharge from the hospital to a location other than LTAC, hospice care or other hospital will be treated as recovered by Day 60. Their time to recovery will be the day of their first observed/imputed recovery score (i.e., 1, 2, 3) or the day of discharge, whichever comes first. Subjects whose last assessment in the study is prior to Day 57 (beginning of Day 60 window) without being discharged from the hospital to a location other than LTAC, Hospice care or other hospital at their last assessment will be considered not recovered and censored at the date of their last assessment.

Endpoint	Analysis	Imputation Method
		
 Death prior to recovery will be considered not recovered and censored at expected study Day 60.
	Supplementary	
 Same imputation method as primary analysis for time to sustained recovery.
	Subgroup	
 Repeat analysis for each subgroup using same imputation as primary analysis for this endpoint.
2. Survival without respiratory failure up to and including Study Day 29	Primary	
 Subjects who complete follow-up without mechanical ventilation or death or who have the event after Day 29 will be considered non-events and censored at Day 29. Subjects whose last assessment in the study is before Day 26 (beginning of Day 29 window) and before experiencing death or progression to mechanical ventilation will be considered non-events and censored at the last assessment. Subjects whose last assessment in the study is before Day 29 but within window for Day 29 (i.e., Day 26, 27, 28) and before experiencing death or progression to mechanical ventilation will be considered non-events regardless of their discharge status and censored at Day 29.
	Primary with Sensitivity Imputation	
 Subjects who complete follow-up without mechanical ventilation or death or who have the event after Day 29 will be considered non-events and censored at Day 29. Subjects whose last assessment in the study is before Day 26 (beginning of Day 29 window) and before experiencing death or progression to mechanical ventilation and were discharged to a location other than LTAC, hospice care, or other hospital will be considered non-events and censored at Day 29. Subjects whose last assessment in the study is before Day 26 (beginning of Day 29 window) and before experiencing death or progression to mechanical ventilation without being discharged to a location other than LTAC, hospice care, or other hospital will be considered non-events and censored at the last assessment. Subjects whose last assessment in the study is before Day 29 but within window for Day 29 (i.e., Day 26, 27, 28) and before experiencing death or progression to mechanical ventilation will be considered non-events regardless of their discharge status and censored at Day 29.
	Sensitivity	
 Same imputation method as primary analysis of this endpoint
	Supplementary	
 Same imputation method as primary analysis of this endpoint
	Subgroup	
 Repeat analysis for each subgroup using same imputation as primary analysis for this endpoint
	Other Secondary Endpoints: Efficacy	
1. Time to 1-point improvement by Day 60	Primary	
 Use the complete data for ordinal score to define time to improvement. Subjects whose last assessment in the study is prior to an observed improvement will be censored at the day of their last assessment. Subjects who complete follow-up but do not experience improvement will be censored at the day of their Study Day 60. Death prior to improvement will be considered not improved and censored at expected study Day 60.
	Subgroup	
 Repeat analysis for each subgroup using same imputation as primary analysis for this endpoint.
2. Time to 2-points improvement by Day 60	Primary	
 Use the complete data for ordinal score to define time to improvement. Subjects whose last assessment in the study is prior to an observed improvement will be censored at the day of their last assessment. Subjects who complete follow-up but do not experience improvement will be censored at the day of their Study Day 60.

Endpoint	Analysis	Imputation Method
		
 Death prior to improvement will be considered not improved and censored at expected study Day 60.
	Subgroup	
 Repeat analysis for each subgroup using same imputation as primary analysis for this endpoint.
3. Clinical status assessed using ordinal scale on Study Days 1, 3, 5, 8, 11, 15, 22, and 29; Change in clinical status using change in ordinal scale from Study Day 1 to Study Days 3, 5, 8, 11, 15, 22 and 29.	Primary	
 Use complete data for ordinal score.
	Subgroup	
 Repeat analysis for each subgroup using same imputation as primary analysis for this endpoint.
4. Days of supplemental oxygen by Study Day 29;	Primary	
 If the subject's clinical status scale is 6 or above at the last observed assessment, then the subject will be considered to be on supplemental oxygen use through Day 29. The endpoint will be total days when assessments are available plus all imputed days following the last observed assessment. If the subject's clinical status is less than 6 at the last observed assessment, then the subject will be considered to not be on supplemental oxygen use for the remainder of follow-up. Thus, no additional imputed days will be added to the number of days recorded on available assessments.
	Subgroup	
 Repeat analysis for each subgroup using same imputation as primary analysis for this endpoint.
5. Days of non-invasive ventilation/high-flow oxygen by Study Day 29;	Primary	
 If the subject's clinical status scale is 6 or above at the last observed assessment, then the subject will be considered to be on non-invasive ventilation/high-flow oxygen through Day 29. The endpoint will be total days when assessments are available plus all imputed days following the last observed assessment. If the subject's clinical status is less than 6 at the last observed assessment, then the subject will be considered to not be on non-invasive ventilation/high-flow oxygen for the remainder of follow-up. Thus, no additional imputed days will be added to the number of days recorded on available assessments.
	Subgroup	
 Repeat analysis for each subgroup using same imputation as primary analysis for this endpoint.
6. Incidence of new non-invasive oxygen use (clinical status > 5) during the study up to and including Study Day 29 for subject with baseline clinical status of 5	Primary	
 If the subject's clinical status scale is 6 or above at the last observed assessment, then the subject will be considered to be on non-invasive ventilation/high-flow oxygen through Day 29. The endpoint will be total days when assessments are available plus all imputed days following the last observed assessment. If the subject's clinical status is less than 6 at the last observed assessment, then the subject will be considered to not be on non-invasive ventilation/high-flow oxygen for the remainder of follow-up. Thus, no additional imputed days will be added to the number of days recorded on available assessments.
7. Days a subject who has a baseline clinical status of 5 has a clinical status > 5 up to and including Study Day 29;	Primary	
 Use complete data for ordinal score to define this endpoint.
	Subgroup	
 Use complete data for ordinal score to define this endpoint.
8. Days of invasive mechanical ventilation/ECMO by Study Day 29;	Primary	
 If the subject's clinical status scale is 7 or above at the last observed assessment, then the subject will be considered to be on invasive mechanical ventilation/ECMO through Day 29. The endpoint will be total days when assessments are available plus all imputed days following the last observed assessment. If the subject's clinical status is less than 7 at the last observed assessment, then the subject will be considered to not be on invasive ventilation/ECMO for the remainder of follow-up. Thus, no additional imputed days will be added to the number of days recorded on available assessments.
	Subgroup	
 Repeat analysis for each subgroup using same imputation as primary analysis for this endpoint.

Endpoint	Analysis	Imputation Method
9. Incidence of new invasive ECMO use through study Day 29 for subjects with baseline clinical status of 5 or 6;	Primary	
 If the subject's clinical status scale is 7 or above at the last observed assessment, then the subject will be considered to be on invasive mechanical ventilation/ECMO through Day 29. The endpoint will be total days when assessments are available plus all imputed days following the last observed assessment. If the subject's clinical status is less than 7 at the last observed assessment, then the subject will be considered to not be on invasive ventilation/ECMO for the remainder of follow-up. Thus, no additional imputed days will be added to the number of days recorded on available assessments.
10. Days a subject who has a baseline clinical status of 5 or 6 has a clinical status > 6 up to and including Study Day 29;	Primary	
 Use complete data for ordinal score to define this endpoint.
	Subgroup	
 Repeat analysis for each subgroup using the complete dataset for ordinal score.
11. Proportion of subjects alive and without respiratory failure at Study Day 29;	Primary	
 Use the complete data for ordinal score to define survival without respiratory failure. Subjects will be considered events at Day 29 if they are dead or are on invasive mechanical ventilation/ECMO anytime between Day 26 and Day 32 (Window for Day 29) regardless of their baseline ordinal score. All subjects who died before Day 26 (beginning of Day 29 visit window) will be considered events. All subjects who died after Day 32 or those who were not on invasive mechanical ventilation/ECMO between Day 26 and Day 32 will be considered non-events.
12. Time (days) to ventilation or death up to and including Day 29;	Primary	
 Use the complete data for ordinal score to define survival without respiratory failure. All subjects whose last assessment in the study is before Day 26 and before progression to mechanical ventilation or death will be considered non-events and censored at the date of their last observed assessment. Subjects who complete follow-up without mechanical ventilation or death will be censored at the expected study Day 29. Subjects whose last assessment in the study is before Day 29 but within window for Day 29 (i.e., Day 26, 27, 28) and before experiencing death or progression to mechanical ventilation will be considered non-events regardless of their discharge status at Day 29.
	Primary with Sensitivity Imputation	
 Use the complete data for ordinal score to define survival without respiratory failure. Subjects whose last assessment in the study is before Day 26 and were discharged to a location other than LTAC, hospice care or other hospital, or progressed to mechanical ventilation or death after Day 29 will be considered non-events and censored at Day 29. Subjects whose last assessment in the study is before Day 26 and before progression to mechanical ventilation or death and without being discharged to a location other than LTAC, hospice care or other hospital at their last assessment will be considered non-events and censored at the date of their last observed assessment. Subjects who complete follow-up without mechanical ventilation or death will be censored at the expected study Day 29.
13. Days of hospitalization from date of admission by Study Day 29.	Primary	
 If a subject is discharged and no further hospitalization data are available, consider the subject as not readmitted, no additional imputed days will be added. If a subject dies while hospitalized, the number of days of hospitalization will be imputed as the number of days between the date of admission and the expected date of subject's Study Day 29 visit+1.
	Subgroup	
 Use complete data for ordinal score to define this endpoint.

Endpoint	Analysis	Imputation Method
Other Secondary Endpoints: Safety		
1. Values of CRP, ferritin, D-dimer, LDH, and fibrinogen on Study Day 1: Study Days 3, 5, 8, 11,15 and 29	Primary	
 If results are not available for any visit day(s) but are available for visits before or after that visit, the average of the two nearest visits will be imputed for all missing visits between them. If a subject dies or is otherwise terminated early from the study, their last available observation will be carried forward. If baseline is missing, another pre-treatment dose will be used, or the earliest post treatment dose will be used.
2. 14-day Mortality	Primary	
 Subjects whose last assessment in the study is before Day 13 (beginning of Day 29 window) and before death will be considered not dead and censored at the date of their last observed assessment. Subjects who complete follow-up will be censored at Day 15. Deaths that occur after Day 15 will be censored at Day 15.
	Primary with Sensitivity Imputation	
 Subjects whose last assessment in the study is before Day 13 (beginning of Day 15 window) and were discharged to a location other than LTAC, hospice care or other hospital, or subjects died after Day 15 will be considered non-events and censored at Day 15. Subjects whose last assessment in the study is before Day 13 (beginning of Day 15 window) and before death and without being discharged to a location other than LTAC, hospice care or other hospital at their last assessment will be considered non-events and censored at the date of their last observed assessment. Subjects who complete follow-up will be censored at Day 15.
3. 28-day Mortality	Primary	
 Subjects whose last assessment in the study is before Day 26 (beginning of Day 29 window) and before death will be considered not dead and censored at the date of their last observed assessment. Subjects who complete follow-up will be censored at Day 29. Deaths that occur after Day 29 will be censored at Day 29.
	Primary with Sensitivity Imputation	
 Subjects whose last assessment in the study is before Day 26 (beginning of Day 29 window) and were discharged to a location other than LTAC, hospice care or other hospital, or subjects died after Day 29 will be considered non-events and censored at Day 29. Subjects whose last assessment in the study is before Day 26 (beginning of Day 29 window) and before death and without being discharged to a location other than LTAC, hospice care or other hospital at their last assessment will be considered non-events and censored at the date of their last observed assessment. Subjects who complete follow-up will be censored at Day 29.
4. 59-day Mortality	Primary	
 Subjects whose last assessment in the study is before Day 57 (beginning of Day 60 window) and before death will be considered not dead and censored at the date of their last observed assessment. Subjects who complete follow-up will be censored at Day 60. Deaths that occur after Day 60 will be censored at Day 60.
	Primary with Sensitivity Imputation	
 Subjects whose last assessment in the study is before Day 57 (beginning of Day 60 window) and were discharged to a location other than LTAC, hospice care or other hospital, or subjects died after Day 60 will be considered non-events and censored at Day 60. Subjects whose last assessment in the study is before Day 57 (beginning of Day 60 window) and before death and without being discharged to a location other than LTAC, hospice care or other hospital at their last assessment will be considered non-events and censored at the date of their last observed assessment. Subjects who complete follow-up will be censored at Day 60.

Endpoint	Analysis	Imputation Method
5. Time to death by Day 29	Primary	
 Subjects whose last assessment in the study is before Day 26 (beginning of Day 29 window) and before death will be considered not dead and censored at the date of their last observed assessment. Subjects who complete follow-up will be censored at Day 29. Deaths that occur after Day 29 will be censored at Day 29.
	Primary with Sensitivity Imputation	
 Subjects whose last assessment in the study is before Day 26 (beginning of Day 29 window) and were discharged to a location other than LTAC, hospice care or other hospital, or subjects died after Day 29 will be considered non-events and censored at Day 29. Subjects whose last assessment in the study is before Day 26 (beginning of Day 29 window) and before death and without being discharged to a location other than LTAC, hospice care or other hospital at their last assessment will be considered non-events and censored at the date of their last observed assessment. Subjects who complete follow-up will be censored at Day 29.
6. SAEs by Day 60	Primary	
 No imputation of missing data will be performed.
7. Grade 3 or 4 AE by Day 60	Primary	
 No imputation of missing data will be performed.
8. Time to Death, SAE or Grade 3 or 4 TEAE by Day 60	Primary	
 Subjects whose last assessment in the study is prior to death or SAE or Grade 3 or 4 TEAE will be censored at the date of their last observed assessment. Subjects who complete follow-up will be censored at Day 60. Deaths that occur after Day 60 will be censored at Day 60.
9. Episodes of early discontinuation or interruption of study product administration;	Primary	
 No imputation of missing data will be performed.
10. Values of WBC with differential, hemoglobin, platelets, creatinine, total bilirubin, ALT, AST, and INR on Study Day 1; Study Days 3, 5, 8, and 11 (while hospitalized); and Study Days 15 and 29 (if attends in-person visit or still hospitalized).	Primary	
 No imputation of missing data will be performed.
Exploratory Endpoints		
1. Concomitant COVID-19 treatments (e.g., steroids) post-baseline up to and including Study Day 29.	Primary	
 No imputation of missing data will be performed. Details regarding imputation of missing dates are provided in Table 8.

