The main analysis of the primary endpoint will be repeated using the ordinal score on Study Days 15 and 29 instead of Day 8 using complete data, adjusting for baseline severity and steroid use. The analysis will be repeated for baseline severity of disease, baseline steroid use, baseline use of emerging COVID-19 treatments, and duration of symptoms subgroups. Each subgroup will be considered separately, and the estimated treatment odds ratio from the proportional odds model with corresponding 95% and 80% confidence intervals and the p-value will be presented for each subgroup. A forest plot will be generated to display the overall treatment odds ratio and CI from each of the within-stratum analyses. Results for Day 15 will be presented in Table 17, Figure 4, and Figure 5 while results for Day 29 will be presented in Table 18, Figure 6, and Figure 7. These analyses will be repeated for the ITT population and results will be presented in Table 20 and Table 21. Odds ratios between the binary progression strata from the proportional odds model are reported in Table 24, Table 25, Table 26, Table 27 for mITT population and ITT population for Study Days 15 and 29.

Oxygenation

Oxygen days will be defined as the number of days where the ordinal score > 4 up to and including Study Day 29. The total number of days will be the sum of all reported days, regardless of whether the days occur consecutively or in disjoint intervals. For planned gaps between study days, the day of the qualifying Study Day and the days to the next planned Study Day will be included in the total number of days. The Post-Discharge Supplemental Oxygen CRF questions regarding days of oxygenation (including ECMO, invasive ventilation, non-invasive ventilation, high-flow oxygen devices, and all other oxygen delivery devices) will be used for any time period the subject is not hospitalized at the study hospital. See Section 6.5 for the plan for handling subjects who do not have data through Study Day 29 or die prior to Study Day 29.

Duration of oxygenation days will be summarized in a table using medians and quartiles by treatment (Table 36). Bee swarm plots of oxygen days by treatment will be generated (Figure 19).

Refer to Table 6 for a list of covariates and subgroup analyses for this endpoint. Refer to Table 7 for imputation methods to be applied to this endpoint.

Non-Invasive Ventilation/High-Flow Oxygen

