^e Supplemental Analysis 1 (age and duration of symptoms prior to enrollment): In addition to the variable included in the model described in ^a, age and duration of symptoms prior to enrollment as additional covariates were added to the model when estimating the OR, 95% CI, 80% CI, and p-values using the same multiple imputation approach as the primary analysis in ^a.

^f Supplemental Analysis 2 (by Baseline COVID-19 treatment category): In addition to the variable included in the model described in ^a, baseline use of COVID-19 treatment as additional covariates were added to the model when estimating the OR, 95% CI, 80% CI, and p-values using the same multiple imputation approach as the primary analysis in ^a. Additional models using use of each COVID-19 treatment category as a covariate separately.

^g For the subgroup analyses, the model described in ^a using complete data was performed for each level of the subgroup.

^h P-Value for treatment difference or P-value from interaction Type III test in subgroup analysis where the interaction between subgroup and treatment is being added to the model.

Tables with similar format:

[Implementation notes: For analyses using Day 15 and Day 29, perform all the analyses using complete data. Delete Primary with Sensitivity Imputation 1 and Primary with Sensitivity Imputation 2 analyses.]

Table 17: Global Odds Ratios for Inferior Clinical Status Score at Study Visit Day 15 Using a Proportional Odds Model — mITT Population

Table 18: Global Odds Ratios for Inferior Clinical Status Score at Study Visit Day 29 Using a Proportional Odds Model — mITT Population

Table 19: Global Odds Ratios for Inferior Clinical Status Score at Study Visit Day 8 Using a Proportional Odds Model — ITT Population

Table 20: Global Odds Ratios for Inferior Clinical Status Score at Study Visit Day 15 Using a Proportional Odds Model — ITT Population

Table 21: Global Odds Ratios for Inferior Clinical Status Score at Study Visit Day 29 Using a Proportional Odds Model — ITT Population

Table 22: Proportional Odds Model for Clinical Status Score at Study Visit 8 – Odds Ratios Between the Binary Progression Strata with Multiple Imputation — mITT Population

OS Table Comparison	Treatment	Lower OS		Higher OS		Odds Ratio OR (80% CI)	Odds Ratio OR (95% CI)	P-value X ²	P-value Fisher's Exact
		n	%	n	%				
1 vs 2-8	Treatment A (N=X)	x	xx.x	x	xx.x	x.xx (x.xx, x.xx)	x.xx (x.xx, x.xx)	0.xxx	0.xxx
	Treatment B (N=X)	x	xx.x	x	xx.x				

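### At Days 15 and 29 the residual missing ordinal scores are filled only by last observation carried forward, and no alternative missing-data analysis remains

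*SAP*

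**What the plan says.** SAP Section 6.5.1 defines a complete-data set for Tables 17, 18, 20, 21 and 24 to 27 and Figures 4 to 7, among others. After rules for intermittent gaps:

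- Deaths: "All missing scores after death will be assigned an ordinal score of 8".
- Subjects discharged anywhere except LTAC, hospice or another hospital: "at their last assessment will be assigned a score of 2 for all timepoints after last assessment".
- Everyone else still missing: "Impute all remaining missing data after last assessment using last observation carried forward".

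Section 8.2.2 says the main Day 8 analysis will be "repeated using the ordinal score on Study Days 15 and 29 instead of Day 8 using complete data". Table 7, row 3 of the other secondary efficacy endpoints, gives one method: "Use complete data for ordinal score". The implementation note under Table 16 (Appendix 1, 14.2) reads "For analyses using Day 15 and Day 29, perform all the analyses using complete data" and then "Delete Primary with Sensitivity Imputation 1 and Primary with Sensitivity Imputation 2 analyses".

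At Day 8 the primary analysis uses multiple imputation for subjects lost without a good discharge (6.5.1, 6.5.2). Carry-forward appears there as Sensitivity Imputation 2.

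**The concern.** The protocol objective (Table 3) is clinical status at Days 15 and 29. Under carry-forward, a subject last seen on Day 4 on supplemental oxygen is analysed as still in hospital on oxygen on Day 29. A subject lost after discharge to hospice can never be counted as dead unless the death is known. At Day 8 the longest possible carry is 8 − 1 = 7 days; at Day 29 it is 29 − 1 = 28. The simpler method therefore stands alone where the gap is longest, and the documents give no reason.

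Two things are at stake. The odds ratio can be biased, and the proportional-odds code for analyses without multiple imputation (6.1) fits a single filled dataset, so imputation uncertainty is ignored.

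Nothing else in the plan covers these days. The tipping-point analysis in 6.5.2 concerns the Day 8 score only. The endpoint review committee adjudicates primary and key secondary endpoints. The site and covariate rows do not test missing-data assumptions.

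**Working it through.** **1. Check on the method (Day 8, SAP Section 5).** Take Table 4 for control and double the cumulative odds for active. Averaging the two arms gives Σp³ = 0.092. With 200 subjects, SE(log OR) = √(12 / (200 × 0.908)) = 0.257, and ln 2 / 0.257 = 2.70. Power is Φ(2.70 − 1.96) = 0.769 at two-sided 0.05 and Φ(2.70 − 1.28) = 0.921 at 0.20, before any futility look. Simulation with the interim rules gives 0.762 and 0.908; Table 5 states 0.765 and 0.913. The plan's figures reproduce.

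**2. Mechanism at one cut.** Suppose 70% of control subjects have a score of 3 or lower, the true OR is 2, and 5% of each arm carry a hospital score of 4 or more.
- True odds: control 0.70/0.30 = 2.333; active 4.667, a proportion of 0.8235.
- After carry-forward: 0.95 × 0.70 = 0.665 and 0.95 × 0.8235 = 0.7824.
- Odds 1.985 and 3.595; OR = 1.81.

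At the cut between category 1 and the rest, with 28% of control in category 1 (40% of 70%), the true odds are 0.389 and 0.778 (active proportion 0.4375). After carry-forward the proportions are 0.266 and 0.4156, the odds 0.362 and 0.711, and the OR 1.96. The common OR averages over cuts, so it shrinks less when category 1 is populated.

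**3. Full model.** The documents give no Day 15 or 29 distribution and no loss rate, so these inputs are assumptions:
- Table 4 shifted so that 50 to 85% of control subjects score 3 or lower;
- category 1 holding 0 to 60% of the category 1+2 mass;
- carried scores of 5, 6 or 7, unrelated to treatment;
- baseline 5 versus 6/7 split 50:50, and adjusted for;
- proportional odds;
- 5% of each arm under carry-forward; true OR 2.

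Fitted OR (shrinkage of the log OR):

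| Category 1 share | 50% recovered | 60% | 70% | 80% | 85% |
|---|---|---|---|---|---|
| 0 (as in Table 4) | 1.89 (8%) | 1.86 (11%) | 1.81 (15%) | 1.73 (21%) | 1.66 (27%) |
| 20% | 1.92 (6%) | 1.90 (7%) | 1.88 (9%) | 1.85 (12%) | 1.83 (13%) |
| 40% | 1.92 (6%) | 1.90 (7%) | 1.88 (9%) | 1.85 (11%) | 1.84 (12%) |
| 60% | 1.92 (6%) | 1.90 (8%) | 1.87 (10%) | 1.84 (12%) | 1.82 (14%) |

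Other populated distributions gave 1.86 to 1.92. A version in which only subjects still in hospital at Day 8 are lost, with their Day 8 score carried forward, gave 1.89 to 1.94.

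**4. Unequal loss.** With 80% recovered and category 1 at 40% of the category 1+2 mass, unadjusted:

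| Carry-forward share, control / active | True OR 1 | True OR 2 |
|---|---|---|
| 5% / 5% | 1.00 | 1.86 |
| 8% / 2% | 1.19 | 2.25 |
| 2% / 8% | 0.84 | 1.54 |

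Other populated distributions moved a null OR to between 1.09 and 1.16 (8%/2%) or between 0.86 and 0.91 (2%/8%).

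**The case against.** The strongest case against the point is that the consequence is small. SAP 6.5.1 expects little missing data and plans chart review for subjects lost to follow-up. Taking the Day 8 SE of 0.257 as a guide, a fall from 2.00 to 1.88 is ln 2.00 − ln 1.88 = 0.062, about a quarter of one SE. The promising and significant thresholds apply to the Day 8 primary endpoint. Mortality, time to ventilation or death, recovery, and survival without respiratory failure through Day 29 have their own sensitivity imputations. All of this stands, and it limits the weight of the point. It does not explain why the same expectation of little missing data led to multiple imputation and a tipping-point check at Day 8 but to neither here.

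The contrast with Day 8 should also not be overdrawn. The Table 16 shell runs the Day 8 subgroup analyses on complete data, and Appendix 2 bases all figures on complete data. The contrast holds for the Day 8 primary analysis. Of the two deleted rows, Sensitivity Imputation 2 is the same rule as the Day 15 and 29 main analysis, so only one real alternative, Sensitivity Imputation 1, is lost.

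A reader might infer that the odds ratio falls by 10% or more once 5% of subjects are lost. The documents do not support that. Deaths and good discharges are scored before carry-forward applies, so 5% lost is not 5% carried forward. If half of those lost fall under the rule, the fall is 2 to 5% (3 to 10% with category 1 empty). With category 1 at 40% of the category 1+2 mass, a 10% fall needs a carry-forward share of about 7% (85% recovered) to 11% (60% recovered).

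**Conclusion.** The structural point holds: single carry-forward is the only missing-data method for the Day 15 and 29 ordinal analyses. With 5% of subjects under the rule equally in both arms and category 1 populated, a true OR of 2 becomes about 1.8 to 1.9, a shrinkage of roughly 6 to 14% on the log scale. It is 8 to 27% if category 1 is empty, and somewhat less if loss occurs only among subjects still hospitalized at Day 8. All of this rests on assumed loss rates and outcome distributions.

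A reader might also infer that the bias is always towards 1. That requires similar loss in the two arms; unequal loss can create an apparent effect where there is none, and no planned analysis at these days would show it. The standard error is understated in every case. The Day 8 decision is not affected.

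**What to change.** In Section 6.5.1, Table 7 row 3, Section 8.2.2 and the Table 16 implementation note, keep death = 8 and good discharge = 2, and use multiple imputation for the remaining missing Day 15 and Day 29 scores. Keep the carry-forward complete-data result as the sensitivity row. The titles of Tables 24 to 27, which exclude multiple imputation, would need to follow.

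The 6.5.2 procedure cannot be reused unchanged. Its model contains treatment, baseline covariates and discharge status but not the last observed ordinal score, so it could not tell a subject last seen at score 4 from one last seen at 7. Its loop also covers last-assessment Days 1 to 8 only. Add the last observed score as a predictor, extend the loop beyond Day 8, and pool sparse late days.

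The cost is SAP wording, modest extra programming, and slightly wider intervals because imputation uncertainty is now counted.
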